6.2.4 Non-Participant STAGE-12 Group Members

STAGE-12 group sessions may be populated with non-participant group members. These individuals are clients in treatment who were not enrolled in the study due to various reasons: beginning treatment prior to the beginning of study recruitment, being ineligible for study participation, or being initially uninterested in the study. CTP clients not interested in participating in the study may subsequently seek an alternative to groups offered at the clinic as part of treatment as usual and may decide to attend STAGE-12 groups. Because these clients are involved in an experimental intervention, they must also provide informed consent or provide verbal consent with an approved information sheet. They must also be made aware of the risks and benefits of group participation. A separate consent form or information sheet is provided for non-study participants.

Non-participant group members are involved primarily to guarantee that group size does not fall below the minimum of 2 participants. To ensure that STAGE-12 groups run continuously throughout the study, each group session may include up to 6 non-participants.

These are their key characteristics:

- Non-participant group members are not considered either STAGE-12 or TAU participants in the study. Essentially, they are "auditing" the STAGE-12 group sessions similar to how students audit a college course: they are not truly "enrolled" in the class but they could gain a benefit from the experience.
- Non-participant group members are consented with a separate consent form or information sheet. They are involved in STAGE-12 group sessions only; they are not involved with STAGE-12 individual sessions.
- Non-participant group members do not have to meet eligibility requirements or meet diagnosis for stimulant abuse or dependence.
- Non-participant group members are not randomized and do not complete research visits or study assessments. No data are collected on individual non-participant group members, though the number of non-participant group members attending each session will be collected.
- Non-participant group members are not compensated for their participation.
- Non-participant group members meet with research staff only for the consent process and to determine the next available group session to attend.
- Non-participant group members may be audio-recorded during the group sessions but the recordings are protected during the study and deleted after procedures have ended, according to local IRB practices. This information is included in the consent form or information sheet.

6.3 Treatment Measures

6.3.1 Quality Control of Treatments Administered

Quality control for the STAGE-12 intervention will be conducted via ongoing review of recordings of group and individual sessions. Adherence scales will be used both for the group and the individual interventions.

Group session adherence scale: Counselor adherence to the structure and content of the protocol in delivery of TSF content of the group sessions will be evaluated following the procedures described by Baker (Baker 1998). Both counselors and supervisors complete parallel adherence rating forms after each session conducted or viewed. The forms consist of Likert-type items covering a range of key TSF interventions (review of recovery tasks, exploration of the patient's use of denial, encouragement to make use of 12-Step programs, etc.). The counselor version of the form is based the TSF Therapist Checklist (Carroll, Nich et al., 1998), and asks the counselor to rate what TSF strategies and interventions were implemented in a given session, and how much the intervention was used. This form has a variety of purposes. First, it is intended to remind the counselor, at each session, of the key ingredients of TSF. Second, it is intended to foster a greater adherence to the manual through self-monitoring of adherence. Third, it can organize and provide the basis for supervision, as the counselor can more readily note and explore with the supervisor the strategies and interventions s/he has trouble implementing with a given participant.

The supervisor version of the form based on the TSF Rating Scale (Carroll, Nich et al., 1998) differs from the counselor version by adding a skillfulness rating for each item. Thus for each intervention, both *quantity* and *quality* are rated. This form is an essential part of training, as it provides structured feedback to the counselor and forms the basis of supervision. It also provides a method of determining whether a counselor in training is ready to be certified to deliver the treatment. When used with ongoing supervision, it enables the supervisor to monitor and correct counselor drift in implementation of the treatment.

Individual session adherence scale: The three individual sessions will be rated using checklists developed for use with the intensive referral procedures. The forms consists of a series of specific activities that counselors are expected to include in each session. For sessions 2 and 3, the specified activities differ depending on whether or not the participant attended a 12-step meeting or not. The counselor indicates which of the elements of the intensive referral strategies and interventions were implemented in a given session. Supervisors can similarly complete the checklist based on their review of session tapes.

6.3.2 Other Procedures to Minimize Potential Biases and Contamination in Administration of Therapies

The threat of cross-contamination is potentially problematic. We will instruct and encourage participants in the STAGE-12 intervention not to share information about the specifics of their treatment with individuals outside of those who are in the intervention group. However, there is no guarantee participants will not discuss their treatment, especially if their treatment raises issues that are then brought into other groups. Likewise, there are concerns about possible cross-contamination coming from program staff (i.e. a counselor learns some of the elements of the STAGE-12 intervention and communicates to other counselors who begin to incorporate elements into other TAU groups). These issues will be addressed in protocol-specific training. Overall, because the STAGE-12 treatment is unique and has many structured sessions and elements, we believe that it is unlikely

participants or staff in the TAU, or those not involved directly with the trial, will be contaminated by casual contact.

6.4 Counselors/Staffing

Two counselors and one supervisor will be selected at each CTP to provide the STAGE-12 intervention. The counselors will each provide the STAGE-12 intervention based on meeting scheduling and caseload, and may also cover TAU sessions as assigned by the CTP. The supervisor will provide fidelity monitoring to the intervention and provide back-up support for group sessions in the event a counselor is unavailable for a scheduled session. All other staff at the CTP will provide the standard treatment.

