Counselors and supervisors will be voluntary participants in the current study. Counselors and supervisors will be required to provide informed consent to be eligible for the study. Each site will require a minimum of two counselors and one supervisor to provide the STAGE-12 intervention and a sufficient number of non-study counselors to maintain the existing TAU services. In addition, CTPs must ensure that the staff participation is fully voluntary; therefore counselors' willingness to participate and their performance in the study will not affect their employment status in any way.

A clinical supervisor will be needed to ensure that counselors are implementing the intervention with an adequate degree of fidelity. The clinical supervisor will fill in for the counselor in the event that the counselor is unavailable. During these periods when the clinical supervisor is seeing participants, he/she will receive supervision from the Lead Node trainer.

The counselor and supervisor trainings require that they attend face-to-face trainings. CTPs will be required to ensure that staff participating in the study will be provided with support to dedicate the necessary effort to complete these trainings and the required training cases in the period of time allowed by the protocol implementation schedule.

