5.3.2.2 Counselor Inclusion/Exclusion Criteria

Counselors and supervisors will be eligible for the protocol who:

- Are credentialed to provide these services in their respective regions,
- Are willing to participate in this study (and sign the informed consent form), complete the counselor assessments, learn and implement a manual guided STAGE-12 intervention and conform to any restrictions placed on TAU during the course of the study,
- Are willing to be randomly chosen to provide the STAGE-12 intervention,
- Are willing to have their sessions recorded and reviewed by a national expert, a supervisor, and/or independent rater; to participate in regular supervision sessions; and to complete process/adherence ratings for the duration of the protocol,
- Are approved by the CTP's administrative/supervisory staff as appropriate for the study (e.g., reliable, competent, likely to be with the CTP for the duration of the study),
- Have a working familiarity with 12 step recovery principles and the self-help groups that utilize them.

Counselors and supervisors will be excluded who:

Are unfamiliar with or negative toward a 12-step orientation to treatment.

All counselors who sign informed consent, meet the criteria above and are interested in participating in this protocol will be part of the pool of counselors from which two will be selected to provide the STAGE-12 intervention. Note that while specific training in the manual-driven TSF or Intensive Referral therapies excludes a counselor from the study, both counselors and supervisors will be required to have working familiarity with 12 step recovery principles and the 12-step recovery self help fellowships (AA, CA and/or NA). The counselor training for the STAGE-12 treatment is designed to work with counselors who are already familiar with the 12-step approach to recovery.

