5.3.3 Participant Selection

5.3.3.1 Inclusion/Exclusion Criteria

Individuals will be eligible for the protocol who:

- Are 18 years of age or older
- Have been admitted to outpatient treatment at a participating CTP which has met the CTP inclusion criteria and have at least 5-8 weeks of outpatient treatment available with an intensity of 5-15 hours of treatment per week.
- Are able to provide consent for study procedures

- Are willing to provide information about their drug and alcohol use
- Have used cocaine, methamphetamine, amphetamine or other stimulant drugs within the past 60 days, or have been incarcerated within the past 60 days and had used stimulants during the 30 days prior to their incarceration
- Meet DSM-IV diagnostic criteria for current (within the last 6 months) abuse or dependence
 of cocaine, methamphetamine, amphetamine or other stimulant drugs as a primary or
 secondary drug of abuse
- Are willing to be randomly assigned to either STAGE-12 or treatment-as-usual and plan to be available for 6 months following randomization
- Are willing to be recorded during group and individual sessions

Individuals will be excluded who:

- Are in need of detoxification for opiate withdrawal (as judged by CTP clinical staff)
- Are seeking detoxification only, methadone maintenance treatment or residential/ inpatient treatment
- Have a medical or psychiatric condition that would, in the opinion of the clinic staff, make participation in this study hazardous
- Have been incarcerated more than 60 days within that past 90 days prior to baseline assessments
- Have pending legal action that would inhibit participation in the study
- Have previously enrolled in the study having met all eligibility criteria

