6.0 TREATMENTS

6.1 Treatment as Usual

Study participants will be enrolled in the currently employed outpatient psychosocial treatment (OPT) in the participating CTPs. The TAU in participating CTPs will likely reflect varying theoretical orientations and treatment philosophies. Many CTPs may reflect a 12-step treatment philosophy and provide encouragement of clients to become involved in 12-step activities. However, it is likely that this effort typically is not applied in a structured or systematic manner. As Carroll, et al. (Carroll, Nich et al. 2000) noted, the structured method of 12-step facilitative interventions is quite distinct from what most CTPs employ. Although discussions about 12-step meetings between staff and patients will take place as they would otherwise, CTP counselors providing TAU will not provide participants the components of the STAGE-12 intervention (either the TSF-based groups or Intensive Referral), including project-prepared handouts, reading material, or journal (and so are not encouraged to write down their plans and reactions regarding 12-step meeting attendance). Participants in TAU also will not be connected to a community-based 12-Step volunteer nor will they receive a list of potential sponsors. These preclusions are consistent with those included in the standard referral/TAU against which Timko's intensive referral condition was evaluated.

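### STAGE-12 counselors may cover TAU sessions with no stated check on what is delivered there, and the exclusion criteria do not address earlier attendance at STAGE-12 groups; both could attenuate the effect

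*Protocol*

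**What the plan says.** **Staffing.** Section 6.4 selects two counselors and one supervisor per site for STAGE-12. The counselors deliver it according to scheduling and caseload, "and may also cover TAU sessions as assigned by the CTP". Section 5.3.1.2 separately requires each site to have "a sufficient number of non-study counselors to maintain the existing TAU services".

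**Limits on TAU content.** Section 6.1 states that "CTP counselors providing TAU will not provide participants the components of the STAGE-12 intervention", and goes on to rule out the project handouts, reading material and journal, the link to a 12-step volunteer and the sponsor list. Section 5.3.2.2 admits only counselors willing to "conform to any restrictions placed on TAU during the course of the study". Section 6.3.2 recognises cross-contamination through participants and through staff, and says: "These issues will be addressed in protocol-specific training". It concludes that it is unlikely that "participants or staff in the TAU, or those not involved directly with the trial, will be contaminated by casual contact".

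**Quality control.** Section 6.3.1 describes review of recordings and adherence ratings for STAGE-12 group and individual sessions. No equivalent is described for TAU sessions.

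**Non-participants.** Section 6.2.4 allows up to 6 non-participants per STAGE-12 group session. They may be clients who started treatment before recruitment opened, who are ineligible, or who at first did not want to join; "CTP clients not interested in participating in the study may subsequently seek an alternative to groups offered at the clinic". They attend groups only, are not randomised, and have no individual data collected. In section 5.3.3.1 the one exclusion about earlier contact with the study is "Have previously enrolled in the study having met all eligibility criteria".

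**The concern.** The primary comparison is between STAGE-12 integrated into TAU and TAU without it. If TAU participants receive active elements of STAGE-12, the difference shrinks, and intent-to-treat analysis carries the shrinkage into the result.

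The counselors in question are taught the manual topic by topic (section 9.3), complete a form after each session that is partly meant to keep the key ingredients in mind (section 6.3.1), and are supervised on adherence (section 9.4). They are the staff most likely to carry the content into another session, even without intending to. If the trial showed no difference, nothing described in the protocol would show how often they had led TAU sessions or what had been delivered there.

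The second gap concerns who is randomised. A client who has already sat through STAGE-12 groups and is then assigned to TAU is not a TAU participant without STAGE-12 in the sense that the comparison intends.

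**Working it through.** **1. Counselors: what restrains content and what verifies it**

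| Provision | What it does | What it leaves |
|---|---|---|
| 6.1 | Bars STAGE-12 components from TAU | A rule with no stated check |
| 5.3.2.2 | Counselors agree to TAU restrictions | Same |
| 6.3.2 | Training; judges casual contact unlikely to contaminate | Its staff example is a counselor passing elements to colleagues, not a STAGE-12 counselor leading TAU |
| 6.3.1 | Recording review and adherence scales | STAGE-12 sessions only |
| 5.1.2.1 | Counselors not selected give no further data | No counselor-level information from TAU |
| 5.4.3.5.2 (TSR) | Participant-reported services, used partly to determine TAU content | Broad service sections, not session content or leader |
| 5.4.3.5.4 (Treatment Tracking Form) | Sessions and hours in both arms | Session leader not mentioned |
| 6.1 (DAPTI) | Clinical Director describes TAU before site initiation | Program level |
| 5.4.3.2.2 (SHAQ) | 12-step activities in both arms | A study outcome, so it cannot also show what a TAU session contained |

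Delivery of STAGE-12 content in TAU is therefore forbidden on paper. What is missing is a way to see whether the rule was kept.

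**2. Prior group attendance: can an exposed client be randomised?**

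- Section 6.2.4 says that non-participants are not enrolled or randomised, so the exclusion for previous enrolment does not reach them.
- Some reasons for being a non-participant can lapse. The incarceration exclusion looks back 90 days, pending legal action can be resolved, and reluctance is described as initial.
- No section says that such a client may be randomised later, and none prevents it.
- With no individual data on non-participants, the study database could not identify the exposure afterwards.

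This exposure precedes randomisation, so it is expected to be equal in the two arms. It reduces the contrast only if the earlier groups had an effect that a later STAGE-12 course does not add again. These clients have had none of the individual sessions.

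**3. Size**

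The protocol gives no contamination rate, and section 10.6 makes no allowance for one. Let c be the fraction of the between-arm difference that is lost. Power is then Φ[(1 − c)·θ − 1.96], where θ is the undiluted standardised effect.

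The stated power is about 85% (200 per arm, effect size 0.42, rho 0.5, attrition 30%). Scaling the table cell of 165 per arm (effect size 0.4, same rho and attrition, 80% power) does not quite reproduce it:

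- Effect size 0.40: θ = (1.96 + 0.842)·√(200/165) = 3.085; power = Φ(1.125) = 87%.
- Effect size 0.42: θ = 3.085 × 0.42/0.40 = 3.239; power = Φ(1.279) = 90%.

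The power graph is not available in the text reviewed, so the difference cannot be traced. All three starting points are shown. For 85%, θ = 1.96 + 1.036 = 2.996.

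| Assumed loss c | From 85% | From 87% | From 90% | Sample size factor 1/(1 − c)² |
|---|---|---|---|---|
| 5% | 81% | 83% | 87% | 1.11 |
| 10% | 77% | 79% | 83% | 1.23 |
| 20% | 67% | 69% | 74% | 1.56 |

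For example, 0.9 × 2.996 − 1.96 = 0.737 and Φ(0.737) = 77%. The values of c are assumptions. The table shows how sensitive power is to dilution, not how much dilution to expect.

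**The case against.** The best defence has four parts.

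*The control condition is protected.* Most of what section 6.1 forbids is tangible or a discrete act: handouts, a journal, a call to a volunteer, a sponsor list. A counselor who has agreed to the restrictions and been trained on them is unlikely to deliver these by accident. A reader might infer that sections 6.1 and 6.4 contradict each other, or that TAU is left open to STAGE-12 content. Neither follows, because 6.4 governs who may staff a session and 6.1 governs what may be delivered in it. What remains is the absence of a check.

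*Later randomisation is nowhere permitted.* A reader might infer that the protocol lets exposed clients into the trial. It is only silent. Section 5.1.1 recruits people seeking admission or being enrolled, and 5.3.3.1 requires at least 5-8 weeks of treatment to be available, so someone already well into treatment is largely outside the frame. This stands as a reason to expect few cases. It does not exclude them.

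*Balanced exposure is not leakage into one arm.* This is correct, and it limits the second gap to a narrowing of the contrast.

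*A strict staffing ban would be costly.* Section 6.2.1 has STAGE-12 participants attending other TAU sessions as well. Where clinic groups mix the arms, an absolute rule would keep two counselors out of any group containing one TAU participant. Nor does the site-level requirement in 5.3.1.2 show that occasional cover is never needed. This stands, and is why the staffing change below is conditional.

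**Conclusion.** The point holds as a modest, inexpensive improvement. STAGE-12 counselors may cover TAU sessions under a written prohibition and training, with no session-level check described for TAU and a reassurance that addresses only casual contact. The exclusion criteria also do not deal with prior attendance at STAGE-12 groups.

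Either gap could move the estimated effect towards zero, provided that STAGE-12 content is active and reaches TAU participants. The counselor gap is the more important: the permission is explicit and the exposure would fall after randomisation, in the control arm. The second is an omission that probably concerns few people.

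The size cannot be estimated from the protocol. A reader might take the power figures above as a forecast that the trial is underpowered. They are not: the loss is assumed, and from the 90% starting point a 10% loss still leaves power above the planned 80%.

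**What to change.** 1. **Section 5.3.3.1.** Add an exclusion: *has attended any STAGE-12 group session as a non-participant*. Check it at screening against the site's non-participant consent or information-sheet records. Because 6.2.4 allows verbal consent with an information sheet, the site needs a record from which attenders can be recognised.
2. **Treatment Tracking Form.** Add the session leader. The form is already completed from clinic records for weeks 1 to 8 in both arms. TAU-arm exposure to STAGE-12 counselors can then be described and used in a sensitivity analysis. That exposure arises after randomisation, so the analysis would support interpretation and would not replace the primary comparison.
3. **Section 6.4.** State that, where the non-study staffing required by 5.3.1.2 allows, STAGE-12 counselors are not assigned to sessions attended by TAU-arm participants.

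The cost is a few lost enrolees, one extra form field and some rostering constraint on two counselors per site. Therapy content does not change.

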7.0 REPORTING AND MONITORING

7.1 Statement of Compliance

This trial will be conducted in compliance with the appropriate protocol, current Good Clinical Practice (GCP), the principles of the Declaration of Helsinki, and all other applicable regulatory requirements. Participating sites must obtain written approval of the study protocol, consent form, other supporting documents, and any advertising for participant recruitment from their local institutional review board (IRB) in order to participate in the study. Prior to study initiation, the protocol and the informed consent documents will be reviewed and approved by an appropriate Ethics Review Committee (ERC) or IRB. Any amendments to the protocol or consent materials must be approved before they are implemented.

